An x-ray of the wrist for the assessment of bone age will be obtained at Screening and at Week 52/Premature Discontinuation visit to determine changes in bone maturation. Sites should use the Greulich and Pyle method for reading the x-ray.²⁰ The x-ray report requires the signature of the radiologist who read the films or of the investigator. The bone age that is determined by the x-ray should be recorded on the eCRF. Assessment of bone age will not be required for subjects with the Premature Discontinuation visit at or before Week 26. An x-ray of the wrist for the assessment of bone age at Screening will

not be required if the subject had an x-ray within 90 days of Screening, provided all protocol required documentation is available at the site.

Anthropometric Evaluations

Height and weight obtained at Baseline, Week 26 and Week 52/Premature Discontinuation will be used by AbbVie Data Management and Statistical groups for determination of BMI and "z" score (observed height velocity [cm/yr] – mean height velocity for age and sex [cm/yr]/SD of the mean) for height.

At Baseline, height from 6 months prior to Screening and maximal weight attained within preceding 6 months will be recorded.

Tanner Stage

Tanner Stage will be assessed at Screening (or at Baseline as appropriate), Week 26 and Week 52/Premature Discontinuation Visit if premature discontinuation occurs after Week 26. Tanner Staging should be captured on the appropriate eCRF page.

Pediatric Ulcerative Colitis Activity Index (PUCAI)

A PUCAI score will also be calculated at all study visits beginning at Baseline.

An example of the PUCAI is located in [Appendix C](#).

The PUCAI score will be assessed using subject-reported symptoms and activity level. The answers should reflect symptoms and activity level during the previous 24 hours. The PUCAI scores of the last 2 days prior to each study visit will be averaged and used for the PUCAI scores for each study visit. The total PUCAI score will be rounded up to the next 5-point interval as applicable. In order to account for unavailable or excluded diary entries as per the provisions given below diary entries for the PUCAI score of the most recent 2 days within 10 days prior to each study visit will be used.

Diary entries of the following days should not be included in the 2 days prior to the visit that are evaluated for the PUCAI score: (1) the day the subject received medication for

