5.3.3 Efficacy Variables

The following definitions are used to describe the primary and secondary variables:

Term	Definition
Clinical response per Partial Mayo Score	defined as a decrease in PMS ≥ 2 points and $\geq 30\%$ from Baseline
Clinical remission per Partial Mayo Score	defined as a PMS ≤ 2 and no individual subscore > 1
Mucosal healing	Endoscopy subscore of 0 or 1
PUCAI remission	defined as < 10
PUCAI response	defined as a decrease in PUCAI ≥ 20 points from Baseline
Clinical remission per Mayo Score	defined as a Mayo Score ≤ 2 and no individual subscore > 1
Clinical response per Mayo Score	defined as a decrease in Mayo Score ≥ 3 points and $\geq 30\%$ from Baseline
Clinical remission per 9 point Mayo Score (without SFS)	defined as a 9 point Mayo Score (without SFS) ≤ 2 and no individual subscore > 1
Clinical remission per 6 point Mayo Score (without SFS and endoscopy subscore)	defined as a 6 point Mayo Score (without SFS and endoscopy subscore) ≤ 1
Clinical remission per 9 point Mayo Score (without PGA)	defined as a 9 point Mayo Score (without PGA) ≤ 2 and no individual subscore > 1
Clinical remission per 6 point Mayo Score (without PGA and endoscopy subscore)	defined as a 6 point Mayo Score (without PGA and endoscopy subscore) ≤ 1
Clinical remission per 9 point Mayo Score (without RBS)	defined as a 9 point Mayo Score ≤ 2 (without RBS) and no individual subscore > 1
Clinical remission per 6 point Mayo Score (without RBS and endoscopy subscore)	defined as a 6 point Mayo Score (without RBS and endoscopy subscore) ≤ 1

Please refer to Section 8.1.4 for details on the sequentially rejective multiple test procedure of the dose groups used in this study versus external placebo for co-primary and ranked secondary endpoints.

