When calculating **PUCAI**, if more than 3 subscores are missing then PUCAI will be considered missing. Otherwise, for missing subscores, the last available post-baseline value for the respective subscore will be carried forward to compute the total PUCAI score. The subscores of abdominal pain, rectal bleeding, stool consistency, number of stools per 24 hours, nocturnal stools and activity level are scored as a 2 day average, rounded to one decimal place. The most recent consecutive days will be used. If consecutive days are not available, then non-consecutive days can be used.

When calculating **IMPACT III** total score, if 4 or more of the items are missing then IMPACT III total score and all subscores will be considered missing. Otherwise, if there are 3 or fewer missing answers, the average of non-missing values will be used to replace the missing items for the total score and subscore calculation. If for subscores consisting of only 3 items (see 'Score Definitions' later in this Section), all of these items are missing and are replaced per above convention, a footnote will be added indicating for how many subjects the subscore included in the analysis has been fully imputed.

When calculating the **WPAI** scores, the following computational notes should be followed.

[figure not shown]
- Define Employment as a binary YES or NO variable where YES corresponds to "Employed" and NO corresponds to "Not Employed":
 - A subject will be considered EMPLOYED at a given visit if Q1 = YES or Q2 > 0 or Q4 > 0.

- A subject will be considered UNEMPLOYED at a given visit if Q1 = NO and no positive hours recorded under Q2 and Q4 (i.e., if Q1 = NO AND $Q2 \le 0$ AND $Q4 \le 0$, then UNEMPLOYED).
- Employment status for a subject will be considered missing at a given visit if Q1 = missing and no positive hours recorded under Q2 and Q4.
- If a subject is UNEMPLOYED or employment status is missing, then S1, S2, and S3 will be set to missing.
- If Q2 = 0 and Q4 = 0 or missing then Q2/(Q2 + Q4) = missing (i.e., S1 = missing).
- If Q2 = 0 and Q4 = 0, then set S3 to missing.
- If Q2 is missing or Q4 is missing, then set S1 and S3 to missing.
- If Q4 = missing, then DO NOT set Q5 = missing.
- If Q5 is missing, then apply the following rules:
 - \circ If Q2 > 0, Q4 = 0, and Q5 = missing, then S3 = 100%.
 - \circ If Q2 = 0, Q4 > 0, and Q5 = missing, then S3 is missing.
 - If Q2 > 0, Q4 > 0, and Q5 = missing, then S3 is missing.

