- Determine if a subject missed work (based on Q2) in order to analyze the proportion of subjects who missed work:
 - Create a binary (YES or NO) "missed work" variable.
 - A subject will be considered as yes to missed work if Q2 is greater than 0.
 - If Q2 = missing, then MISSED WORK = missing.
 - \circ If Q2 > 0, then MISSED WORK = YES
 - \circ If Q2 = 0, then MISSED WORK = NO
 - Therefore, the proportion of subjects who missed work will be counted based on the number of subjects with MISSED WORK = YES.

Partial Study Dates: If the day and/or month are missing, the following conventions will be used to impute the missing visit (or assessment) dates other than the dosing dates:

- 01 for missing start day,
- End of month for missing end day,

- January 1st will be used for a missing start month,
- December 31st for missing end month.

In case of partially missing AE start and stop dates, the dates will be imputed by comparing to first dose date of study medication so that the corresponding AEs will be made treatment-emergent whenever possible.

In case of missing or partially missing study drug dosing dates, the dates will not be imputed. Subjects will be considered as not receiving dose on that date.

[figure not shown]
Rounding

Rounding will be performed only for presentation of results. No rounding will be performed before or during analyses/calculations. The ROUND function of SAS will be used to round results for presentation.

The mean and median will be rounded for presentation to one decimal more than the data were entered into the database. For example, mean systolic blood pressure will be presented to one decimal place (125.2 mmHg) when it is recorded to integer level in the database (110 mmHg). The standard deviation will be rounded to two decimal places more than the data were entered into the database (e.g., 25.31 mmHg for systolic blood pressure). The minimum and maximum values will be presented as entered into the database.

Probabilities will be rounded to three decimal places before assignment of statistical significance and will be presented in rounded format. Probabilities that round to zero or are reported by SAS as zero will be presented as '< 0.001.'

Percentages will be rounded for presentation to one decimal place; e.g., the proportion 0.1244 will be reported in percent as 12.4%.

Score Definitions

1. Mayo Score and Component Scores

 Table 2.
 Definition of Mayo Score and Component Scores

Term	Definition

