Clinical remission per Partial Mayo Score	PMS \leq 2 and no individual subscore $>$ 1
Mucosal healing	Endoscopy subscore of 0 or 1
Clinical remission per Mayo Score	Mayo score ≤ 2 and no individual subscore > 1
Clinical response per Mayo Score	Decrease in Mayo Score ≥ 3 points and $\geq 30\%$ from Baseline
Clinical remission per 6 point Mayo Score (without SFS and endoscopy subscore)	Defined as the 6 point Mayo Score (without SFS and endoscopy subscore) ≤ 1
Clinical remission per 9 point Mayo Score (without SFS)	Defined as the 9 point Mayo Score (without SFS) \leq 2 and no individual subscore $>$ 1
Clinical remission per 6 point Mayo Score (without PGA and endoscopy subscore)	Defined as the 6 point Mayo Score (without PGA and endoscopy subscore) ≤ 1
Clinical remission per 9 point Mayo Score (without PGA)	Defined as the 9 point Mayo Score (without PGA) \leq 2 and no individual subscore $>$ 1
Clinical remission per 6 point Mayo Score (without RBS and endoscopy subscore)	Defined as the 6 point Mayo Score (without RBS and endoscopy subscore) ≤ 1
Clinical remission per 9 point Mayo Score (without RBS)	Defined as the 9 point Mayo Score \leq 2 (without RBS) and no individual subscore $>$ 1

2. **PUCAI**

Pediatric Ulcerative Colitis Activity Index (PUCAI) is calculated as the sum of six subscores [each being a 2 day average, see above] of PUCAI (abdominal pain [no pain = 0, pain can be ignored = 5, pain cannot be ignored = 10], rectal bleeding [none = 0, small amount with < 50% of stools = 10, small amount with most stools = 20, large amount with > 50% of stool content = 30], stool consistency of most stools [formed = 0, partially formed = 5, completely unformed = 10], number of stools per 24 hours [0 to 2 = 0, 3 to 5 = 5, 6 to 8 = 10, > 8 = 15], nocturnal stools [no = 0, yes = 10], activity level [no limitation = 0, occasionally limited = 5, severe restriction = 10]) with maximum total score 85. Higher scores represent more severe disease.

- PUCAI remission is defined as PUCAI < 10.
- PUCAI response is defined as a decrease in PUCAI \geq 20 points from Baseline.

3. **IMPACT III**

The IMPACT III questionnaire assesses quality of life in IBD related fields and comprises 35 closed questions with a 5-point Likert scale for all answers ('good' through 'bad' answers scored by 5 through 1; range of total score 35 - 175, higher scores suggesting higher quality of life).

Total Score: sum of Q1 - Q35

Subscores:

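### The protocol rounds the PUCAI total up to the next 5 points and the SAP does not, so the same diary entries can give different remission or response results in exploratory endpoints

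*SAP*

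**What the plan says.** Protocol 5.3.1.1 (PUCAI paragraph) builds the visit score in two steps. First, "The PUCAI scores of the last 2 days prior to each study visit will be averaged". Second, "The total PUCAI score will be rounded up to the next 5-point interval as applicable".

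SAP 6.0 builds it differently. Under the missing-items rules for questionnaires, the six subscores "are scored as a 2 day average, rounded to one decimal place". Under Score Definitions, PUCAI "is calculated as the sum of six subscores [each being a 2 day average, see above] of PUCAI". Neither place rounds the total. The Rounding paragraph of the same section adds: "No rounding will be performed before or during analyses/calculations".

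The two documents apply the same cut-offs to the score. In the SAP, "PUCAI remission is defined as PUCAI < 10". Response, in Protocol 5.3.3 and equally in the SAP, is "defined as a decrease in PUCAI ≥ 20 points from Baseline".

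The SAP's summary of changes (12.0) does not mention dropping the 5-point round-up.

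**The concern.** The two documents share thresholds but apply them to differently constructed scores. A programmer working from the SAP would produce a PUCAI that is not the one the protocol defines, and nothing in the SAP would show it.

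The endpoints at stake are:

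- five of the eleven comparisons of high against standard dose (Protocol 8.1.4.2, SAP 10.4): PUCAI remission at Week 8, PUCAI response at Week 8, both again at Week 52, and steroid-free PUCAI remission at Week 52;
- PUCAI remission and response over time;
- change from Baseline in PUCAI and the correlation of PMS with PUCAI, which use the score itself and not the remission or response flags.

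For the flags, the direction is fixed within each endpoint. Relative to the protocol, the SAP rule can only add remitters and can only remove responders.

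**Working it through.** The plan states no figure that depends on this rule, so there is none to reproduce. The check is whether the two definitions ever disagree, and where.

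**Inputs.** Item levels are in Protocol Appendix C and SAP 6.0. For example, "abdominal pain [no pain = 0, pain can be ignored = 5, pain cannot be ignored = 10". The full set is abdominal pain 0/5/10, rectal bleeding 0/10/20/30, stool consistency 0/5/10, number of stools 0/5/10/15, nocturnal stools 0/10 and activity level 0/5/10. The maxima sum to 10 + 30 + 10 + 15 + 10 + 10 = 85, the maximum that both documents give. There are 3 × 4 × 3 × 4 × 2 × 3 = 864 possible daily patterns. Planned arm sizes (SAP 4.3) are 46 high and 31 standard at Week 8, and 28 high and 29 standard at Week 52.

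**Step 1: the scores before rounding the total.** Let A and B be the two daily totals. Averaging is linear, so the SAP's sum of item averages is T = (A + B)/2, the same as the protocol's two-day average. Every item moves in steps of 5 or 10, so A and B are multiples of 5 and T is a multiple of 2.5. Rounding item averages to one decimal changes nothing, because they are already multiples of 2.5. The only difference left is the protocol's final step, P = 5 × ceil(T/5).

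**Step 2: remission (below 10).**

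| SAP total T | Protocol total P | SAP remission | Protocol remission |
|---|---|---|---|
| 0 | 0 | yes | yes |
| 2.5 | 5 | yes | yes |
| 5 | 5 | yes | yes |
| 7.5 | 10 | yes | no |
| 10 | 10 | no | no |

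Above 10 neither rule gives remission. Enumerating all 864 × 864 pairs of daily patterns confirms that the rules differ only at T = 7.5, that is, daily totals of 5 and 10 or of 0 and 15, in either order. One example is activity level scored 5 on one day and 10 on the other, with every other item 0.

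**Step 3: response (fall of at least 20).** Call a total half-step if it ends in 2.5 or 7.5. Rounding up adds 2.5 to a half-step total and nothing to any other.

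- Baseline and visit both half-step, or neither: the fall is the same under both rules.
- Only the baseline half-step: protocol fall = raw fall + 2.5. A raw 17.5 becomes 20 and crosses the threshold.
- Only the visit half-step: protocol fall = raw fall − 2.5. A raw 22.5 becomes 20 and still qualifies; a raw 17.5 becomes 15 and fails under both rules.

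The only disagreement is therefore a raw fall of exactly 17.5 from a half-step baseline. For example, 47.5 to 30 is 17.5 under the SAP (no response) and 50 − 30 = 20 under the protocol (response). Over the 35 attainable totals from 0 to 85 there are 35 × 35 = 1225 baseline–visit pairs. The rules disagree in 14 of them, all in this direction. These pairs are not equally likely, so 14/1225 is not a probability.

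**Step 4: size of one changed classification, by arm.**

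- Week 8: 1/46 = 2.2 points (high), 1/31 = 3.2 points (standard).
- Week 52: 1/28 = 3.6 points (high), 1/29 = 3.4 points (standard).
- Steroid-free PUCAI remission: larger, because only subjects on corticosteroids at Baseline count. The documents do not give that denominator.

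**The case against.** The best defence is that the SAP is silent and does not contradict the protocol. Its introduction says it elaborates the protocol's methods, it never withdraws the round-up, and the protocol qualifies its rule with the words as applicable. On this view the protocol step carries over. Nor is the SAP's ban on rounding absolute, since the same section rounds subscores to one decimal.

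This does not hold. The SAP gives a complete formula for the total and follows it with "No rounding will be performed before or during analyses/calculations", so carrying the round-up over would breach the SAP's own text. The protocol's qualifier most naturally covers averages that are already multiples of 5. The one-decimal subscore rounding sits awkwardly with the ban but, by Step 1, has no numerical effect.

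Three points on the other side do stand. Every PUCAI endpoint is exploratory (Protocol 5.3.3.2, SAP 10.4). The documents give no distribution of PUCAI scores, so the frequency of disagreement cannot be estimated. And a diary total of 7.5 does not always change the result: under non-responder imputation (SAP 6.0) a subject already re-randomized for disease flare is a non-responder whatever the score.

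**Conclusion.** The conflict is real, undeclared and narrow. Remission differs at one attainable visit total, 7.5. Response differs at one pattern, a raw fall of 17.5 from a half-step baseline. Each changed classification, among subjects not already set to non-response, is worth about 2.2 or 3.2 points in an arm at Week 8 and 3.6 or 3.4 points at Week 52. These figures rest on the planned arm sizes and on complete item scores in the published steps.

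A reader might infer more, and the documents do not support it:

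- *That the trial's main conclusions are exposed.* No co-primary or ranked secondary endpoint, external placebo comparison, significance level or power figure uses PUCAI.
- *That the SAP has inflated remission and deflated response.* It can only move them in those directions. Whether it moves them at all depends on data the documents do not contain, and the number of affected subjects could be zero.

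It should be corrected because the repair is cheap and because a defined score should not depend on which document the programmer opens.

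**What to change.** In SAP 6.0, state that after the two-day averaging and any carry-forward of missing subscores, the six subscores are summed and the total is rounded up to the next multiple of 5 before the remission and response definitions are applied. Rounding the sum, and not averaging two daily totals, keeps the rule compatible with the SAP's carry-forward, because a daily total may not exist when a subscore is missing. Add an explicit exception to the Rounding paragraph; otherwise the SAP would contradict itself.

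The alternative is to keep the unrounded total and declare and justify it as a departure from Protocol 5.3.1.1. Either way, one rule should be fixed before analysis.

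The cost is a sentence or two of text and a line of code. If the protocol rule is adopted, PUCAI remission may fall slightly and PUCAI response may rise slightly.

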- Bowel symptoms (7 items: Q1, Q3, Q10, Q19, Q21, Q25, Q31)
- Systemic symptoms (3 items: Q6, Q28, Q32)
- Emotional functioning (7 items: Q4, Q5, Q11, Q12, Q13, Q16, Q29)
- Social functioning (12 items: Q8, Q9, Q14, Q17, Q18, Q20, Q23, Q26, Q27, Q30, Q34, Q35)
- Body image (3 items: Q7, Q15, Q33)
- Treatment/interventions (3 items: Q2, Q22, Q24)

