10.4 Secondary Efficacy Analyses

[figure not shown]
The secondary efficacy endpoints are divided into two groups. The first group consists of ranked secondary efficacy endpoints. The second group includes all other secondary efficacy endpoints and special assessments.

The ranked secondary efficacy endpoints in hierarchical order are:

[figure not shown]
- Proportion of subjects in Mayo clinical response at Week 52 in Week 8 responders per PMS;
- Proportion of subjects who achieve mucosal healing at Week 52 as measured by Mayo endoscopy subscore (defined as ≤ 1) in Week 8 responders per PMS;
- Proportion of subjects who achieve Mayo clinical remission at Week 52 in Week 8 remitters per PMS;
- Proportion of subjects receiving systemic corticosteroids (UC related or non-UC related) at Baseline who have discontinued systemic corticosteroids prior to Week 52* and are in Mayo clinical remission at Week 52 in Week 8 responders per PMS.

Additional exploratory secondary analyses will be performed for:

[figure not shown]
- Proportion of subjects in PMS clinical remission at Week 52 in Week 8 responders per PMS;
- Proportion of subjects in PUCAI remission (defined as < 10) at Week 8;
- Proportion of subjects in PUCAI response (defined as a decrease in PUCAI
 ≥ 20 points from Baseline) at Week 8;

- Proportion of subjects in PUCAI remission (defined as < 10) at Week 52 in Week 8 responders per PMS;
- Proportion of subjects in PUCAI response (defined as a decrease in PUCAI
 ≥ 20 points from Baseline) at Week 52 in Week 8 responders per PMS;
- Proportion of subjects receiving systemic corticosteroids at Baseline who discontinue systemic corticosteroids prior to Week 52* and are in PUCAI remission at Week 52 in Week 8 responders per PMS;
- Change from Baseline in total IMPACT III Quality of Life score and subscores over time for subjects at least 9 years old at Baseline;
- Change from Baseline in WPAI scores over time;
- Change from Baseline in "z" scores for height at Week 26 and Week 52;
- Change from Baseline in BMI at Week 26 and Week 52;
- Change from Baseline in "z" scores for weight-for-age at Week 26 and Week 52;
- Proportion of subjects at appropriate Tanner stage (see Section 6.0) at Baseline, Week 26 and Week 52 (OC analysis);
- Proportion of subjects in PMS response over time;
- Proportion of subjects in PMS remission over time;
- Proportion of subjects in PUCAI response over time;
- Proportion of subjects in PUCAI remission over time;

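### IMPACT III gaps are filled from the whole questionnaire even for subscores, so a 3-item subscore can be analysed with no answer from its own domain, while four gaps anywhere delete complete subscores.

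*SAP*

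**What the plan says.** The rule is in SAP 6.0 under missing items on questionnaire scales. It uses one count of missing items over all 35 questions.

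- Four or more missing: "if 4 or more of the items are missing then IMPACT III total score and all subscores will be considered missing".
- Three or fewer missing: "the average of non-missing values will be used to replace the missing items for the total score and subscore calculation".
- For 3-item subscores, the SAP foresees that "all of these items are missing and are replaced per above convention". In that event "a footnote will be added indicating for how many subjects the subscore included in the analysis has been fully imputed".

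The score definitions in SAP 6.0 list six subscores. Three have 3 items each: Systemic symptoms, Body image and Treatment/interventions. Bowel symptoms and Emotional functioning have 7 each, and Social functioning has 12.

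SAP 10.4 lists among the additional exploratory analyses: "Change from Baseline in total IMPACT III Quality of Life score and subscores over time for subjects at least 9 years old at Baseline". The protocol (synopsis and section 5.3.3.2) names only the total score, so the subscores enter through the SAP. The questionnaire is completed at Baseline and Weeks 8, 26 and 52 or premature discontinuation.

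**The concern.** A subscore is reported to show one domain separately from the others. If its missing items are filled with the child's mean over all domains, it moves towards that child's overall level and a problem confined to one domain is partly hidden. In a 3-item subscore, one gap makes a third of the score come from elsewhere and three gaps make all of it.

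The deletion rule errs in the other direction. Gaps confined to one domain remove subscores that the child answered in full. The sample is small: SAP 4.3 plans 57 adalimumab subjects in maintenance, and only children aged 9 or older at Baseline complete IMPACT III.

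The SAP's other conventions are stricter. In the same section, a missing PUCAI subscore is filled from an earlier value of that subscore, and a Mayo score with a missing subscore is not imputed. SAP 6.0 also says that missing Baseline data are in general not imputed. The IMPACT III rule has no Baseline exception, so a filled-in subscore could serve as the reference for change.

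**Working it through.** **Which average is meant.** The SAP does not say in words that the average covers the whole questionnaire. The provision for a 3-item subscore with no answered item settles it: a within-domain mean does not exist there, so the value must come from other domains. That the average is taken per child is the natural reading, though not stated.

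**Item lists.** 7 + 3 + 7 + 12 + 3 + 3 = 35, with Q1 to Q35 each used once. Items are scored 1 to 5, so the total runs from 35 to 175, as the SAP states.

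**Assumptions for the illustration.** The SAP gives a sum only for the total. I assume subscores are also sums, so a 3-item subscore runs from 3 to 15, a range of 12 points. The documents give no item means. I take 4.2 for the 32 items outside Body image and let the body-image items truly average a gap g below that, with g = 0.5 or 1.7.

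**All three body-image items missing.** The form has three gaps, so it is scored. Each gap receives 4.2, giving 3 × 4.2 = 12.6. The error is 3g.

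- g = 0.5: truth 3 × 3.7 = 11.1; error 1.5; 1.5/12 = 12.5%.
- g = 1.7: truth 3 × 2.5 = 7.5; error 5.1; 5.1/12 = 42.5%, about 43%.

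**One body-image item missing.** The mean is over 34 answered items, two of them from Body image. The error is g × 32/34.

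- g = 1.7: mean (32 × 4.2 + 2 × 2.5)/34 = 139.4/34 = 4.1; score 2 × 2.5 + 4.1 = 9.1 instead of 7.5; error 1.6; 1.6/12 = 13%.
- g = 0.5: error 0.5 × 32/34 = 0.47; 0.47/12 = 4%.

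**Deletion.** Suppose 4 of the 12 Social functioning items are blank and the other 31 items are answered. The count reaches four, so the total and all six subscores are set to missing, although five of the six domains are complete.

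**What happens to a deleted subscore.** SAP 10.1 uses LOCF for continuous endpoints unless otherwise noted.

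- Weeks 26 and 52: an earlier post-baseline value would normally be carried forward in place of the answers given at that visit.
- Week 8: there is normally no earlier post-baseline IMPACT III value, and SAP 6.0 forbids carrying Baseline forward, so the child drops out of that visit's analysis.
- Baseline: the child is excluded from the change analysis (SAP 6.0).

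**The case against.** The strongest objection concerns weight. The subscores are exploratory, outside the multiple test procedure in SAP 10.1, and not among the eleven endpoints compared between high and standard dose in SAP 10.4. They are reported only as change from baseline with 95% CIs by group. This stands and limits the importance of the point.

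Second, the worst case is narrow: all three items of one small domain blank, at most three gaps in the form, and a large gap between domains. Protocol 10.2 has site staff verify completion of the paper questionnaires, which should keep gaps few. This also stands. It is why a range is shown, and why the 43% should not be read as an expected error.

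Third, the SAP foresees full imputation and discloses it. This helps only in part. The footnote counts fully imputed 3-item subscores but leaves them in the means and CIs. It does not cover subscores with one or two items filled from elsewhere, or complete subscores that were deleted.

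Fourth, a reader might infer that every child with four gaps is lost to the subscore analysis. The documents do not support that: under SAP 10.1, LOCF would normally keep the child in at Weeks 26 and 52, though with an older value.

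Finally, a reader might infer that the rule departs from the instrument's scoring instructions. The documents do not reproduce those instructions and the SAP cites no manual for the rule, so this cannot be judged.

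**Conclusion.** The concern holds as a minor defect in an exploratory analysis. The SAP text leads to subscores that contain no answer from their own domain and to the deletion of subscores answered in full.

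For a wholly missing Body image score the illustrative error is 12.5% to 43% of the range, for true gaps of 0.5 to 1.7 points per item. For one missing item it is 4% to 13% over the same gaps. These figures rest on summed subscores and assumed item means. How often items are missing is not given, so the effect on group results cannot be sized.

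It might be tempting to conclude that the rule weakens the trial's efficacy findings. It does not: neither co-primary endpoint and none of the ranked secondary endpoints uses IMPACT III.

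**What to change.** In SAP 6.0:

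1. Keep the rule of four or more missing items for the total score only.
2. For each subscore, replace a missing item by the child's mean of the answered items of that same subscore when enough of its items are answered. At least half would mean 2 of 3, 4 of 7 or 6 of 12. This threshold is a proposal, to be checked against the instrument's scoring instructions.
3. If too few are answered, set only that subscore to missing.
4. Delete the provision that lets a fully imputed 3-item subscore into the analysis, together with its footnote.

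In the deletion example above, all six subscores could then be scored, five of them with no imputation.

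The cost is a few sentences in the SAP and a small change to the scoring program. A few 3-item subscores that would now be filled from other domains become missing, or at Weeks 26 and 52 are filled by LOCF. In those cases one imputation replaces another, but the carried value comes from the same domain.
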